The final analysis results will include plots of the prior and posterior on the $\log(RR)$ and RR scales. Although the most complete inference from each of the above defined prior-to-posterior analyses are the posterior distributions, the posteriors will be summarized by calculating $\Pr(RR \leq 1)$ and $\Pr(\log(RR) \leq 0)$ using each prior. Also, the posterior distributions for RR will be summarized by calculating equal-tail-area 95% credibility intervals for $\log(RR)$ and RR . If $\Pr(RR \leq 1) > 0.9$ after using the skeptical prior, then the claim will be that the data contains sufficiently strong evidence against a null hypothesis that it should convince a reasonable skeptic, if the skeptic believes the data to be the output of an unbiased and well conducted study. Similarly, if $\Pr(RR \leq 0.8125) < 0.1$ after using the enthusiastic prior, the claim will be that the data contains sufficiently strong evidence against a hypothesis stating the true effect is as large as hypothesized during original sample size calculations.

The model given on the next page will be fit in WinBUGS to estimate the relative risk as well as the uncertainty in the parameter estimates. Note: the model is given in a form that uses non-informative priors, but skeptical and enthusiastic priors will also be applied as defined above. The parameter estimates of this model will be generated by

fitting five MCMC chains. Each chain will involve 10,000 burn-in samples and 200,000 additional samples, which will be thinned by a value of 10. The result will be 100,000 useable samples to estimate the Posterior distributions necessary for making inference about the relative risk.

```

model{

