Note that the treatment in this trial will be conducted during the first few weeks of life for most study subjects, while the primary outcome of death or neurodevelopmental impairment will be assessed at 18-22 months of age. Thus, interim monitoring for this trial will be based primarily on monitoring adverse events (chiefly, death). For the first 120 randomized enrollees, the DCC will track rates of neonatal mortality and generate pre-specified tables after each 30 enrollees reach the Network Status (death, discharge, transfer or 120 days of age). Thereafter, if no trends of differences between groups were to develop, these comparisons will be done after every 60 enrollees reach Network status. The computed statistic at each of these safety looks will be compared to Pocock boundaries that are constructed beforehand so that an overall alpha level of 5% is maintained. If any trends of differences between groups were to develop, the DCC would notify the DSMC.

There will be annual DSMC meetings convened to monitor the progress of the trial and review the accruing safety data, starting one year after at least 11 sites have IRB clearance to start enrolling into the trial. Once follow up data start becoming available (which should occur from the 2nd year onwards) interim efficacy data will also be presented to the DSMC. To control for the inflation of Type I error associated with sequential testing, O'Brien-Fleming boundaries will be calculated. Since we cannot precisely predict beforehand what proportion of trial enrollees will have primary outcome data available before each of these meetings, we will use Lan DeMets spending functions to adjust the O'Brien-Fleming sequential monitoring bounds to account for unequally spaced interim analyses. In order to ensure the safety of participants, this monitoring regime ensures that adverse events are monitored more frequently than measures of efficacy, and the statistical bounds used to detect group differences in adverse event rates are more liberal than those used to determine efficacy. All data presented to the DSMC will be blinded to treatment group, though the report may be unblinded at the DSMC's request.

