4. patient is at a center able to perform both laparotomy and drainage.

Exclusion Criteria:

1. Major anomaly which influences likelihood of developing primary outcome or affects surgical treatment considerations;
2. congenital infection;
3. Prior laparotomy or peritoneal drain placement,

4. Prior NEC or IP,
5. Follow-up unlikely (e.g., mother incarcerated, or currently resides (or plans to move) far from any Network center.), and
6. Infant for whom full support is not provided (including surgical treatment).

Method of Treatment Assignment and Randomization

Infants enrolled into the randomized cohort will be randomized using a variable, permuted, block size scheme. Infants will be randomized by calling RTI International as soon as a decision to perform surgery is made (or via a computer randomization process). Randomized infants will be stratified according to two variables: center and according to the overall risk for death or NDI (higher / lower). The risk stratification formula was primarily developed in the prospective observational model and includes the following variables: birth-weight, gestational age, vasopressor requirement (yes / no), if infant is on high frequency (oscillating or jet) ventilation or not (any modality of conventional ventilation or no mechanical ventilation), pH, FiO₂, and preoperative diagnosis (NEC or IP). Treatment beyond the initial surgical management will be unaffected by the trial.

Treatment Masking

As this is a surgical trial, the surgeons will not be masked to randomized treatment. Outcome assessments at 18-22 months will be assessed by evaluators who are masked to the details of the operative intervention(s) that have been performed using standard Network assessments. The statistician is unmasked in this trial.

Sequence of Planned Analyses

Interim Analyses

Annual Data Safety Monitoring Committee (DSMC) meetings will be convened to monitor the progress of the trial and review the accruing safety and efficacy data. Starting one year after at least 11 sites have IRB clearance to start enrolling into the trial, safety data will be monitored. Once follow up data start becoming available (which should occur from the 2nd year onwards) interim efficacy data will also be presented to the DSMC. All figures, summaries, and listings created in the interim analyses and presented to the DSMC will be masked to treatment assignment, but interim analysis results will be unmasked at the DSMC's request.

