The treatments in this trial will be conducted during the first few weeks of life for most study subjects, while the primary outcome of death or neurodevelopmental impairment will be assessed at 18-22 months of age. As a consequence, to ensure the safety of participants and trial integrity, interim analysis will be completed using both safety and efficacy data but an emphasis will be placed on adverse events and other safety measures.

The interim analysis plan described below ensures that adverse events are monitored more frequently than measures of efficacy, and the statistical bounds used to detect group differences in adverse event rates are more liberal than those used to determine efficacy. The safety monitoring will consist of summary adverse event tables and a mortality monitoring scheme that uses Pocock type sequential testing boundaries. The scheme for monitoring the primary efficacy variable will use Lan-DeMet's spending functions to implement O'Brien-Fleming type boundaries while accounting for unequally spaced interim analyses. Lan-DeMet's spending functions will be used to estimate the boundaries at each interim efficacy analysis, because we cannot precisely predict beforehand what proportion of trial enrollees will have primary outcome data available before each of the annual DSMC meetings.

Adverse events during the course of the trial treatment period will be prospectively monitored, as will clinical morbidities throughout hospitalization. The enrolled population is extremely high risk, and their hospitalization can produce a great number of expected adverse events and clinical diagnoses. Rates of these events, historically observed among similar extremely low gestation/birth weight infants, will be provided to the DSMC.

The set of clinical outcomes monitored were:

- Death
- Number of surgeries
- Surgical complication
- Parenteral alimentation
- Days on parenteral alimentation
- Days in hospital
- Severe IVH
- PVL
- Seizures
- PDA prior to enrollment
- PDA treated
- EOS
- LOS
- ROP
- BPD

- Death or serious morbidity (Hosp.)
- Death or Severe IVH
- Death or sepsis
- Death or ROP
- Death or BPD
- Causes of Death
 - CNS insult
 - Gastrointestinal
 - Immaturity
 - Infection
 - Malformation
 - Pulmonary
 - Other

For each of the above conditions, summary tables will tabulate counts by treatment group and cohort, but these summaries will not include inferential statistics such as p-values or confidence intervals.

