Interim Mortality Assessment

In addition to the annual production of safety summaries suitable for presentation to the DSMC, interim analyses using Pocock type group sequential boundaries will be used to monitor group differences in mortality. For the first 120 randomized enrollees, the DCC would track rates of neonatal mortality after each 30 enrollees reach the Network Status (death, discharge, transfer or 120 days of age). Thereafter, if no trends of differences between groups develop, these comparisons will be done after every 60 enrollees reach Network status. Per the protocol, the computed statistic at each of these safety looks will be compared to Pocock boundaries that are constructed prior to any interim analysis so that an overall alpha level of 5% is maintained. If any trends of differences between groups develop, the DCC would notify the DSMC and present them an unplanned interim analysis report.

The Pocock boundaries for the interim analysis of mortality were calculated by using the `gsProbability` function in the `gsDesign` package for R. For boundary calculations, a scenario of six interim looks plus one final analysis was considered. The following code was used:

```
library(gsDesign)
gsProbability(k=7, theta=0, n.I=c(30, 60, 90, 120, 180, 240, 300),
             a=rep(-2.516, 7), b=rep(2.516, 7))
```

The output from this call to `gsProbability` was:

Analysis	N	Lower bounds		Upper bounds	
		Z	Nominal p	Z	Nominal p
1	30	-2.52	0.0059	2.52	0.0059
2	60	-2.52	0.0059	2.52	0.0059
3	90	-2.52	0.0059	2.52	0.0059
4	120	-2.52	0.0059	2.52	0.0059
5	180	-2.52	0.0059	2.52	0.0059
6	240	-2.52	0.0059	2.52	0.0059
7	300	-2.52	0.0059	2.52	0.0059

Boundary crossing probabilities and expected sample size assume any cross stops the trial

Upper boundary

	Analysis							Total	E{N}
Theta	1	2	3	4	5	6	7		
0	0.0059	0.0045	0.0035	0.0029	0.0032	0.0027	0.0023	0.025	291

Lower boundary

	Analysis							Total
Theta	1	2	3	4	5	6	7	
0	0.0059	0.0045	0.0035	0.0029	0.0032	0.0027	0.0023	0.025

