Once the model is fit, the treatment test-statistic, a z statistic, will be compared to the interval $\{-2.516, 2.516\}$. If the test statistic for the treatment effect in the primary interim mortality model is within the $\{-2.516, 2.516\}$ interval, then per protocol no report will be given to the DSMC. On the other hand, if the test statistic is outside of this interval, then a basic interim mortality analysis report will be produced for the DSMC. The interim mortality analysis report will consist of:

- Treatment effect relative risk ratios from robust Poisson regressions and 95% CIs for all complete infant cohorts (1st 30, 1st 60, 1st 90, etc.).
- Fisher exact test results for comparison of Low/High baseline risk distributions for all complete infant cohorts.
- Frequency tables of mortality by treatment for Low/High baseline risk, with interpretative statements based on the robust Poisson regression model that took into account the treatment by baseline risk interaction.

Any report sent to the DSMC will also contain safety summary tables typically reported in the annual DSMC meetings.

In addition to the above analysis, the interim safety analysis will also include two secondary analyses. First, the observed distributions of High/Low risk within each group will be estimated and compared using Fisher's exact test. Second, a robust Poisson regression of death at time of Network status as a function of treatment, baseline risk, and the interaction between treatment and baseline risk will be completed. This interaction model will have the form:

$$y_i | (s_i, r_i, c_i) \sim \text{Poisson}[\lambda(s_i, r_i, c_i)] \text{ where}$$

$$\log[\lambda] = \alpha + \beta \cdot s_i + \gamma \cdot r_i + \gamma_2 \cdot s_i \cdot r_i + \nu_c \cdot c_i .$$

Interim Efficiency Assessment

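### Does the SAP withhold mortality differences from the DSMC under a no-report rule that the protocol does not contain?

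*SAP*

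**What the plan says.** The protocol (Interim Monitoring) has the coordinating center track neonatal mortality in the first 120 randomized infants and "generate pre-specified tables after each 30 enrollees reach the Network Status". The next step reads "Thereafter, if no trends of differences between groups were to develop, these comparisons will be done after every 60 enrollees reach Network status". Each look's statistic is compared with Pocock boundaries built to hold overall alpha at 5%. The sentence that follows is "If any trends of differences between groups were to develop, the DCC would notify the DSMC".

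The SAP (Interim Mortality Assessment) repeats this sequence and ends it with "If any trends of differences between groups develop, the DCC would notify the DSMC and present them an unplanned interim analysis report". For the boundary, "a scenario of six interim looks plus one final analysis was considered", at 30, 60, 90, 120, 180, 240 and 300 infants, which gives ±2.516. Later in the same section it sets the working rule. Outside ±2.516, a mortality report is produced for the DSMC. Inside, "then per protocol no report will be given to the DSMC".

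Separately, both documents provide annual DSMC meetings. The SAP (Interim Analyses) lists death first among the monitored outcomes, with counts by treatment group. What the DSMC receives "will be masked to treatment assignment, but interim analysis results will be unmasked" if it asks, and "these summaries will not include inferential statistics such as p-values or confidence intervals".

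**The concern.** Three things look wrong.

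- **Attribution.** The SAP cites the protocol for a no-report rule, and the protocol has none.
- **Undefined trigger.** If a trend is anything weaker than a boundary crossing, the SAP gives two instructions for a result inside ±2.516: notify the DSMC, and do not report.
- **Look schedule.** The same undefined word decides whether looks move to every 60 infants after the first 120. Neither document gives the spacing if a trend does appear, yet ±2.516 was computed for seven fixed looks.

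The protocol (Sample Size) names a large neonatal mortality difference as a ground on which the DSMC might stop the trial. The stakes would therefore be a delayed safety signal and a monitoring alpha above 5%.

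A side issue is that both documents call the safety bounds more liberal than the efficacy bounds, without qualification. The SAP's own efficacy bounds at 225 and 300 infants (2.34 and 2.02) are lower than 2.516.

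**Working it through.** **1. The plan's boundary.** Inputs are the SAP's looks at 30, 60, 90, 120, 180, 240 and 300 infants and constant bounds of ±2.516. Recursive integration under the null gives upper crossing probabilities of 0.0059, 0.0045, 0.0035, 0.0029, 0.0032, 0.0027 and 0.0023, the same as the SAP's table. The total is 0.02505 per side, or 0.0501 overall. The boundary is right for this schedule.

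**2. Alpha if the schedule changes.** Suppose looks stayed at every 30 infants up to 300. There would be ten looks, and ±2.516 would give 0.0552. That spacing is an assumption found in neither document. Keeping it only when one of the first four looks shows a trend gives, by simulation under the null:

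| Assumed meaning of a trend | Overall alpha |
|---|---|
| \|z\| > 2.3 | 0.051 |
| \|z\| > 1.96 | 0.052 |
| \|z\| > 1.645 | 0.053 |
| \|z\| > 2.516 (a crossing) | 0.050 |

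In the last row, extra looks can come only after a crossing that has already been counted as an error, so nothing is added.

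**3. What goes unreported at a look.** With equal arms of n infants, a and b deaths and no covariates, z = log(a/b) / √(1/a + 1/b − 2/n).

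- 37/60 against 23/60: log(1.609) = 0.4754; √(0.02703 + 0.04348 − 0.03333) = 0.1928; z = 2.47. RR is 1.61 (95% CI 1.10 to 2.35). Inside, so no report.
- 38/60 against 23/60: z = 2.63. Outside, so reported.
- 54/90 against 37/90: z = 2.48. Inside.
- 70/120 against 51/120: z = 2.41. Inside.

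**4. How long it stays unreported.** Start from 37/60 against 23/60 at 120 infants and enumerate all outcomes of the next 30 infants per arm:

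| Assumed true mortality | Inside at 180 | Reported at 180 |
|---|---|---|
| 62% v 38% | 18% | 82% |
| 60% v 40% | 25% | 75% |
| 55% v 45% | 55% | 45% |
| 50% v 50% | 82% | 18% |

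The protocol expects 320 infants in 4 years, or 80 a year. Looks 30 infants apart are 30/80 = 0.375 years (4.5 months) apart, and looks 60 apart are 9 months apart. The annual meeting limits the wait to about 80 further infants, and that many only if every look in between stays inside.

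**5. The side issue on liberal bounds.** A mortality look needs Network status, at most 120 days (0.33 years) after enrollment when age at entry is ignored. An efficacy look needs at least 22 months (1.83 years).

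- Last mortality look: 300/80 + 0.33 = 4.1 years.
- Efficacy look at 225: 225/80 + 1.83 = 4.6 years or later.

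While mortality is being monitored at planned accrual, the only efficacy bounds in use are 4.05 and 2.86. Both exceed 2.516, so the sentence is true in practice and too broad only as written.

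**The case for a change.** The strongest case for a change is that this is the main safety endpoint, and its reporting rule should not rest on an inference. The protocol puts the boundary comparison and the notification in separate sentences and never equates them. A reader who takes a trend in its ordinary, weaker sense would expect the DSMC to hear about RR 1.61 with an interval excluding 1. The annual tables are no full substitute, being masked by default and without inferential statistics. The choice of meaning matters too: over seven looks under the null, the chance of at least one notification is 5% at 2.516, 18% at 1.96 and 32% at 1.645 (the last two thresholds are illustrative).

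Part of this stands. The attribution to the protocol is inaccurate, the definition is missing, and so is the spacing after a trend.

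It does not follow that the plan misdirects anyone. Notification is the only consequence either document attaches to the boundary comparison before the SAP spells out its rule. If a trend were not a crossing, the protocol's boundary would have no function. The SAP says its purpose is to set out the protocol's analyses in more detail, and the ±2.516 rule does that.

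The near-miss examples show only that a threshold has cases just inside it. They also use an unadjusted z, whereas the SAP's model adjusts for baseline risk and, if possible, center. Sending tables to the DSMC at every look would be a new duty that the protocol does not impose. Limiting contact between meetings to boundary crossings is a legitimate design choice.

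**Conclusion.** No change follows. The SAP's rule can be carried out as written, and with a trend read as a crossing of ±2.516 it agrees with the protocol and holds overall alpha at 5%. Even on looser readings with an assumed 30-infant spacing, alpha is 0.051 to 0.053, and at most 0.055 if that spacing always applied. A real mortality difference of the size in the example would probably be reported one look later. A smaller true difference could take longer, with the annual review of deaths by group as the backstop.

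This rests on the natural reading of the notification sentence, on planned accrual of 80 infants a year, and on unadjusted illustrations. What is left is a loose attribution, an unwritten definition and one sentence that is too broad. They could be tidied if the documents were reopened for other reasons. Doing so would not alter any boundary, analysis or conclusion.

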
Analysis & Interpretation. The primary outcome (death or NDI at 18-22 months corrected age) will be analyzed in standard logistic regression equations in which the predictor variables include center, and level of risk at enrollment as determined by the method described above. Separate analyses will be used to assess whether there is an interaction between treatment (laparotomy or drainage) and disease (NEC or IP). Secondary analyses of randomized patients will be performed using Bayesian methods to assess the (posterior) probability that laparotomy reduces death or NDI relative to that with drainage.

Consent to randomization may be unobtainable before surgery for a sizable proportion of infants. Providing parents at least agree to collection of the same baseline and outcome data as for randomized infants, we will relate surgical treatment to risk adjusted outcome. A finding that the risk adjusted relative risk in the nonrandomized patients is similar to the relative risk observed in the randomized patients will support the validity of the trial results and generalizability of the results among randomized patients to nonrandomized patients. (This would be expected based on a prior meta analysis of studies using a comprehensive cohort design [JAMA 2005]). Whether use of propensity scoring also supports the results among randomized patients will also be assessed.

Sample Size and Resources. Based on our observational study, we hypothesize that 80% of drain infants and 65% of the laparotomy infants will die or be impaired (NNT = only 7 to gain one unimpaired survivor); 300 infants (150 / group) whose primary outcome is determined will be needed (alpha =0.05 & beta = 0.20, two sided Fisher exact test). Enrollment will likely require 4 years (assuming a consent rate of 50%) unless the consent rate is higher than projected. We propose to initiate this trial within Network sites initially given the importance and urgency of the clinical question. Enrollment will be prospectively monitored and if found to be low after 6 months (after 80% of participating centers have IRB approval and are actively participating in the trial), consideration will be given to add additional sites. Despite the difficulties anticipated with the proposed trial, the total expense and effort required will be small relative to other Network trials, and the trial may facilitate future trials involving urgent/emergent therapies, rare diseases, or surgical interventions.

TRIAL OBJECTIVES

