the Bayley tests. We plan to critically examine these data (GDB data, pooled data from NEST study subjects, and publicized data from other studies) at yearly intervals during the trial enrollment period. The sample size determination will be reevaluated, and may be revised upwards as the uncertainty regarding the Bayley III lessens (2 years after study commencement). These decisions will be made by the Steering Committee based upon a recommendation by the NEST subcommittee, and without any knowledge of the difference between the two treatment groups in this trial with regard to the proportion of impaired children.

Sample Size. Allowing for a smaller difference between treatment groups in the trial than in our observational study, we hypothesize that 80% of the drain group and 65% of the laparotomy group will die or be impaired at 18-22 mo. (Number needed to treat = only 7 to gain one unimpaired survivor from laparotomy). By PASS software, a total sample size of 300 infants who have their outcome assessed is needed with $\alpha = 0.05$ and $\beta = 0.20$ using 2-sided Fisher exact test.

In the observational study 156 infants were enrolled in 14 centers in 18 months. By extrapolating these numbers to a 16-center trial design, 120 eligible patients / year would be expected. Based on the latest GDB data, using the 16 centers prior to reformatting the Network, an estimated number of eligible babies of 190 is obtained. Our best estimate of the number of eligible patients in the new 16-center Network is 160 / year. We anticipate a 50% enrollment rate, $\geq 95\%$ consent for data collection (as for generic data collection), equal use of initial laparotomy and drains; and a 50% mortality in each group. Assuming a consent rate of 50%, 320 patients would be enrolled in a 4-year period with 160 deaths and 160 survivors. With a 90% follow up rate, 144 survivors would have the primary outcome measured. This would yield 304 patients which will meet our sample size requirement during a 4-year enrollment period. If the consent rate is below 50%, the enrollment period would need to be extended.

We propose that the trial be stopped when any of the following are met: 1) DSMC might stop trial for large difference in neonatal mortality (secondary outcome), which is unlikely given equivalent survival in both observational study and two randomized trials; 2) 300 randomized patients are enrolled and have primary outcome assessed; or 3) a 5-year enrollment period has elapsed.

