To control the Type I error associated with sequential testing of the primary efficacy endpoint, O'Brien-Fleming boundaries will be calculated for three interim and one final analysis. Since we cannot precisely predict beforehand what proportion of trial enrollees will have primary outcome data available before each of these meetings, we will use the Lan DeMets approximation to the O'Brien-Fleming sequential monitoring bounds to account for unequally spaced interim analyses. Original power calculations based on Fisher's exact test indicated that 150 infants per arm would be sufficient for 80% power if 80% and 65% of infants experienced death or NDI in the Drain and Laparotomy arms respectively. Additional simulations were used to estimate power using the following interim analysis plan and a robust Poisson regression model to estimate treatment effect, under the above-mentioned trial assumptions. The estimated power was 82%.

Interim efficacy assessments will be completed at approximately 75, 150, and 225 randomized infants who are at least 22 months corrected age regardless of death. A final analysis will occur at 300 randomized infants and will account for the earlier looks. The following R code was used to predict the O'Brien-Fleming boundaries under these assumptions:

```
library(gsDesign)
OF.design <- gsDesign(k=4, test.type=2, n.I=c(75, 150, 225, 300),
                      sfu="OF")
OF.design$upper$bound
```

In this call to `gsDesign()`, "k" equals the total number of planned efficacy analyses (interim + final), "test.type" equals 2 so the design is two-sided with symmetrical boundaries, and "sfu" equals OF to indicate O'Brien-Fleming boundaries. Note that only an upper bound spending function was specified since the design is symmetrical. The above call to the `gsDesign` function resulted in the following boundaries:

Interim Analysis	Lower Boundary	Upper Boundary
1	-4.05	4.05
2	-2.86	2.86
3	-2.34	2.34
4	-2.02	2.02

Since this design is two-sided and not 'closed', it is possible that the study could end without one arm being identified as better than the other. As such, the potential 'beta'

error in this design is the failure to reject a false null hypothesis and not the failure to accept a false null hypothesis.

Because actual enrollment at the time of each interim efficacy analysis will not occur exactly as planned, boundaries will be recalculated using the following R code:

```
OF.update <- gsDesign(k=L, test.type=2, n.I=vec.L, sfu=sfLDOF,

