maxn.IPlan=300)
OF.update$upper$bound
```

where L equals the total number of completed and still to complete looks such as 4, and $vec.L$ contains a modified list of sample sizes at the exact and still to be completed looks such as $c(81,150,225,300)$. Note that the spending function is now “sfLDOF”, which specifies that the boundaries will be recalculated given new sample size points based on the Lan-DeMets approximation of O’Brien-Fleming boundaries.

At the time of each interim analysis, the boundaries for the current and future interim analyses will be updated using `gsDesign()` as described above. A robust Poisson regression model will be used to analyze the primary outcome of death or NDI at 18-22 months. For the robust Poisson regression, the outcome for the i^{th} infant will be:

$$y_i = \begin{cases} 0 & \text{for survival without NDI} \\ 1 & \text{for death or survival with NDI} \end{cases}$$

The covariates will have the form:

$$s_i = \begin{cases} 0 & \text{initial surgery was drain} \\ 1 & \text{initial surgery was laparotomy} \end{cases}$$

$$r_i = \begin{cases} 0 & \text{low baseline risk for death or NDI} \\ 1 & \text{high baseline risk for death or NDI} \end{cases}$$

The model will have the form:

$$y_i | (s_i, r_i, c_i) \sim \text{Poisson}[\lambda(s_i, r_i, c_i)], \text{ where } \log[\lambda] = \alpha + \vartheta \cdot s_i + \gamma \cdot r_i + \nu_c \cdot c_i \text{ and } c_i \text{ represents the site for the } i^{\text{th}} \text{ infant among } C \text{ total sites.}$$

Similar to the safety interim analysis, the test statistic produced for the treatment effect will be a z-statistic. This z-statistic will be compared to the appropriate boundary pair calculated from the updating call to `gsDesign()`. The actual robust regression modeling at each interim analysis will be completed in SAS, and a figure summarizing the interim

analysis results will be constructed in Excel. Prior interim analysis results will be represented in the figure as well.

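### The SAP counts 300 randomised infants where the protocol counts 300 with a known outcome, and its coding rules disagree on survivors whose NDI is undetermined

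*SAP*

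**What the plan says.** **Count.** The protocol counts infants with a known outcome in three places. Its abstract (Sample Size and Resources) says "300 infants (150 / group) whose primary outcome is determined will be needed". Its Sample Size section says "a total sample size of 300 infants who have their outcome assessed is needed". The stopping rule in that section applies when "300 randomized patients are enrolled and have primary outcome assessed". Enrolment is planned separately: 320 infants, 160 deaths and 160 survivors, then "With a 90% follow up rate, 144 survivors would have the primary outcome measured", giving 304.

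The SAP (Interim Efficiency Assessment) puts its interim looks at about 75, 150 and 225 "randomized infants who are at least 22 months corrected age regardless of death", and then states "A final analysis will occur at 300 randomized infants and will account for the earlier looks". The boundary-update code carries "maxn.IPlan=300". From a simulation of this plan the SAP reports "The estimated power was 82" per cent.

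**Coding.** Four places in the SAP bear on survivors whose NDI is not known:
- NDI Adjudication sends infants with too little information from the visit to masked review. It uses the result in the primary analysis and treats those still unresolved as missing.
- The efficacy model in Interim Efficiency Assessment gives zero only to survival without NDI.
- Primary Analysis of Randomized Cohort Data calls its model identical to one on pages 17 and 18, apparently that efficacy model. It then gives one to death or NDI and zero to all others.
- The secondary-analysis section lists imputation of NDI, if possible, among sensitivity analyses for adjudicated outcomes.

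**The concern.** Randomised and assessed infants are different counts here, because some survivors will not be assessed. If the final analysis is tied to 300 randomised, the information falls below what the protocol's sample size assumes. The missing infants are also not a random subset: death is always a known outcome, so every infant without an outcome is a survivor. Leaving them out raises the event risk in both arms and moves the risk ratio toward one.

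The coding conflict concerns the same infants. A programmer who follows the primary-analysis section literally would count a survivor with no visit as an unimpaired survivor, which is the favourable result. One who follows the other two sections would set that infant to missing. The SAP says that the statistician and coordinating centre are not masked, so this choice should be fixed in writing and not settled at programming.

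**Working it through.** **Inputs from the documents.** Event risks 80% drain and 65% laparotomy (RR 0.65/0.80 = 0.8125). Mortality 50% in each arm and follow-up of survivors 90% (Protocol, Sample Size). Bounds ±4.05, ±2.86, ±2.34, ±2.02 at four looks (SAP, Interim Efficiency Assessment).

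**Step 1: reproduce the stated figures.**
- Two-sided Fisher exact test, full enumeration, 150 per arm: 80.3% (stated 80%).
- Four looks with the SAP bounds, z = log(RR) / √[(1−a)/(n₀a) + (1−c)/(n₁c)], where a and c are the observed drain and laparotomy risks, treatment only, all 300 outcomes known: 82.3% (stated 82%).
- Yield: 320 × (0.50 + 0.50 × 0.90) = 304 (stated 304).

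The stated power figures therefore match calculations in which every outcome is known.

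**Step 2: outcomes from 300 randomised.** 300 × 0.95 = 285. Conversely, 300 known outcomes need 300/0.95 ≈ 316 randomised.

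**Step 3: expected risks.** With mortality m, follow-up f and true risk p:
- Left out: [m + f(p−m)] / [m + f(1−m)]. Drain 0.770/0.95 = 81.1%; laparotomy 0.635/0.95 = 66.8%; RR 0.825.
- Coded zero: m + f(p−m). Drain 77.0%; laparotomy 63.5%; RR 0.825.

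**Step 4: four-look power, unadjusted** (200,000 or more simulated trials per row, standard error about 0.1 point).

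| Scenario | Left out | Coded zero |
|---|---|---|
| 300 randomised, 90% follow-up | about 77% | about 71% |
| 316 randomised | about 79% | about 74% |
| 320 randomised | about 80% | about 74% |
| 300 randomised, 85% follow-up (assumed) | about 74% | about 65% |
| 300 randomised, 95% follow-up (assumed) | about 80% | about 77% |
| 300 randomised, mortality 55% drain / 45% laparotomy (assumed; same 80% and 65% totals) | about 79% | about 78% |

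To split the 5-point fall with infants left out: 285 outcomes at the undiluted risks give about 80.3%, so the count costs about 2 points. The other 3 or so come from dilution, which does not go away at 300 assessed (about 79.5%).

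**Step 5: adding centre.** The SAP default model includes centre. A smaller simulation (4,800 trials, standard error about 0.6 point, 16 centres assumed, three assumed sizes of stratum effect) gave 83.5–85.8% with complete data, 78.9–80.5% left out and 73.4–74.9% coded zero. Type I error in that model was 5.5–6.0%, so part of its gain comes from a slightly liberal test.

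**Step 6: unequal loss with no true effect.** Assume survivor follow-up of 95% drain and 85% laparotomy, with 50% mortality. At a null risk of 80%, coded zero gives (0.5 + 0.85 × 0.3)/(0.5 + 0.95 × 0.3) = 0.755/0.785 = 0.96. Left out gives (0.755/0.925)/(0.785/0.975) = 1.01.

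| Null risk in both arms | Type I error, coded zero | Type I error, left out |
|---|---|---|
| 80% | about 9% | about 5.4% |
| 72.5% | about 7% | about 5.9% |
| 65% | about 5.5% | about 6.2% |

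The order reverses across the protocol's own range of risks.

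**The case against.** **Coding.** Giving one to an event and zero to the rest is ordinary shorthand for an indicator variable. The adjudication section has a specific missing-data rule for the primary analysis, and the primary-analysis section declares its model identical to one that reserves zero for survival without NDI. Two specific rules outweigh one loose phrase. This largely stands: a reader might infer that the SAP plans to count lost survivors as unimpaired, and the documents do not support that. What remains is narrower. The adjudication rule starts from insufficient information at a follow-up visit and does not expressly cover survivors with no visit. The rule against imputation is limited to the interim analyses. For survivors with no visit, the only coding sentence that reaches them in the final analysis is the literal one.

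**Count.** The sentence placing the final analysis at 300 randomised does not end enrolment. The protocol's stopping rule governs that, and the SAP holds all final analyses until the last randomised infant has died, withdrawn or reached follow-up status. Boundaries are recalculated from actual numbers. All of this stands, so the text does not show that the trial stops short. It does not merge the two counts, however, because a withdrawn infant satisfies the waiting condition without supplying an outcome.

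**Size.** Most of the 5-point fall is dilution that the protocol's own count shares, and the loss from zero coding depends on mortality being equal in the arms. Both points stand and are reflected in the verdict.

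**Conclusion.** Both inconsistencies are in current text and should be reconciled. Neither overturns the design.

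The count discrepancy is modest. On the protocol's mortality and follow-up assumptions it amounts to about 15 outcomes and about 2 points of power. With dilution, unadjusted power is about 77% at 300 randomised and about 79–80% at 316–320. With centre in the model it stays near 80%. The stated 80% and 82% are not wrong for 300 known outcomes, although the SAP does not give its simulation's settings for missing data or covariates.

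The coding conflict could matter more, but only if the literal wording is followed. Power would then be about 71% with equal 50% mortality, a loss of about 11 points. It would be between 77% and 78%, a loss of about 5 points, if mortality were 55% and 45% with the same totals. Setting undetermined survivors to missing is the likelier intent.

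A reader might also infer that unequal loss between arms is by itself a reason to prefer missing over zero. It is not: under the assumed 95%/85% imbalance both codings inflate type I error, and which is worse depends on the null risk. The case for correcting the wording rests on consistency with the SAP's own definition of the outcome and on not counting unknown results as favourable.

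**What to change.** **Coding.** In Primary Analysis of Randomized Cohort Data, replace the catch-all zero with: *zero for survival without NDI; missing if NDI is undetermined, including survivors with no visit*. This brings the section into line with the adjudication rule and the efficacy model, and costs one sentence.

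**Count.** In Interim Efficiency Assessment, use one count throughout: infants with the primary outcome determined, both for the sample sizes at every look and for the planned maximum of 300. Keep the 22-month age condition, regardless of death, only to select which infants are eligible for a look. This needs about 316–320 randomised, which the protocol's plan of 320 already covers, although its five-year enrolment limit could bind first. Alternatively, keep 300 randomised, re-run the power simulation with 90% follow-up of survivors and restate the result. That costs one re-run of an existing simulation.

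**Optional.** Extend the imputation already listed in the secondary-analysis section to all survivors with undetermined NDI, as a sensitivity analysis beside the complete-case result. Its drawback is the assumption that loss among survivors is random given the covariates used.
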